12.2. Potential Risks

There is the potential for low risks to participants associated with this research project:

12.2.1 Breach of confidentiality: Assessment procedures could reveal sensitive information about participants' medical history and history of alcohol/drug use. Risk of breach of confidentiality is possible, though highly unlikely. Specifically, if a participant tells research staff that she is planning to harm herself or her children, the research staff will report this information to the appropriate agency, as required by law. Other than the need to report those incidents that are regulated by mandatory reporting laws (the reportable STIs in Michigan are Chlamydia and Gonorrhea), we feel that there is minimal risk to participants with regard to other breaches in their confidentiality.

12.2.2 Coercion: Coercion occurs when potential participants feel compelled to participate in research for reasons such as perceived demand or the availability of large sums of reimbursement. This can be particularly true when there is little benefit to the individual for their participant (not an issue in this study). In the present study, the inclusion of a protected population and protection from coercion is of the utmost importance.

12.2.3 Discomfort: Participation in the study may lead to psychological distress due to the sensitive nature of questions regarding disclosure of STI and/or alcohol/drug use during pregnancy the related negative social and psychological consequences. There are no physical risks conferred by urine testing for the sensitive nucleic acid amplification tests to be conducted to diagnose the STIs of interest. However, testing for any sexually transmitted disease can involve the psychological burden of finding out one has an infection that needs treatment or having a false positive test result.

Adequacy of Protection Against Risks

At each point of contact in the study, participants will be reminded of the alternative of not participating in the study (or once enrolled, to discontinue participation), and will be informed that their care at Michigan Medicine clinics, or any care within Michigan Medicine and in any other follow-up medical care at the clinics and/or Michigan Medicine will in no way be affected by their decision to participate or not to participate in the study. Moreover, we will provide referral information to all participants at each point of contact. Further procedures to minimize each of these risks are described below.

12.3. Protection Against Risk

We will take the following steps to protect against risks associated with this research project:

We will minimize the risk of breach of confidentiality. A Certificate of Confidentiality will be obtained from the National Institutes of Health prior to the commencement of research. The purpose of this certificate is to protect the identity of research subjects participating in studies that collect sensitive information. Potential participants will be informed that a Certificate of Confidentiality has been obtained for this project and that this certificate will protect the investigators from being forced to release any research data in which participants can be identified, even under court order or subpoena, although this protection is not absolute. Potential participants will be informed of the situations in which they may not be protected under the Certificate of Confidentiality. No information about participants will be released without their permission or where required by law. This approach has been successfully carried out by Drs. [name] and [name] in previous studies involving women in the perinatal period.

Risk of social or legal consequences as a result of disclosure of STIs and/or alcohol/drug use during pregnancy will be dealt with in several ways. We will minimize the potential risks due to loss of confidentiality by strictly adhering to the guidelines for research outlined by the University of Michigan IRB, Michigan state law and the DHHS Federal Policy for the Protection of Human Subjects (45 CFR Part 46 Subpart D). As described in the previous section, there will be full informed consent prior to participation in the study (a two-part consent process). Participant data will be encrypted in transit between user and server. No identifying information will be entered into the CIAS software; the software will designate a unique participant code for each participant. Additionally, all forms with participant information will be marked with a code number and not with the participant's name. The link between the participant code number and name will be securely stored on the HIPAA-compliant database REDCap, which is administered and managed through the Michigan Institute for Clinical Research (MICHR) at the University of Michigan. This database will only be accessible by the Study Coordinator and study staff. Lastly, potential participants will

be informed of the situations in which they may not be protected under the Certificate of Confidentiality. Participants will also be informed about the risk of loss of confidentiality due to the STIs screens. No information about participants will be released without their permission or where required by law. Further, we have confirmed with Child Protective Services (CPS) of the Michigan Department of Health and Human Services, that they do not respond to reports of substance use during pregnancy unless the report is of a newborn infant with alcohol/drug in its system. Further, per the Michigan Department of Health and Human Services guidelines, there is no mandatory reporting of the disclosure of alcohol or drug use during the postpartum assessments.

Possible distress due to sensitive items will be noted clearly in the informed consent information sheet (for screening) and in the written informed consent form (for participants). All participants will be told that they can skip any question, test, or quit at any time if they become uncomfortable. To further address possible distress due to sensitive items, participants will be asked by the computer program if anything the computer has asked or done is making them feel upset right now. The computer program will notify the research team at completion of study if any participant answers yes to this question, in addition to notifying the research team if the participant has endorsed any items indicative of possible need/desire for further assistance. (Note that the computer program will not provide details regarding any answers, only that there is a need to follow-up with the participant verbally to evaluate the need for assistance). At a minimum, all participants indicating some distress will be given a list of referral options that will include information on how to contact a Michigan Medicine social worker. We will minimize the psychological burden associated with STI tests (i.e., trichomoniasis, chlamydia trachomatis, and neisseria gonorrhoea).

Participants face the risk of increased psychological distress due to the research procedure of STI testing and distress due to a positive test for one of the selected STIs or having a false positive test result. All women will be informed that they do not need to be tested for the selected STIs, if it poses too much distress for them. They will be reminded that they can discontinue participation at any time. Moreover, as mentioned in the section above, clinical backup will be provided during all assessments and during the intervention phase of the study by a licensed clinician to help facilitate the stabilization and referral process for participants who decompensate during assessment procedures.

At any phase of the study (i.e., during the follow up assessments), participants who test positive for any of the three STIs or with a recurrent STI will be referred for comprehensive STI care to their treating physician or health care provider at Michigan Medicine (if participant is a Michigan Medicine patient). For Michigan Medicine patients, [name] (Co-I), study physician, will facilitate treatment according to the 2015 CDC STD Treatment Guidelines or will refer patient to another physician who will provide treatment and counseling free-of-charge to the participant. If the STI is reportable, it will be reported to the Health Department as required by law. Results of STI testing and any subsequent treatment or referrals will also be confidentially communicated to the participant's health care physician, if the participant requests this transfer of information. Participants will be asked to sign a medical release of information for this purpose. The study will arrange and cover transport costs for participants without transport who need these follow-up appointments for STI treatment. Research staff will assist participants in addressing any barriers to accessing treatment and will follow-up with participants to confirm that treatment was received. For participants who test positive and are not Michigan Medicine patients, [name] will write a prescription for the appropriate treatment which will be available at a Michigan Medicine Pharmacy. Should they prefer to seek treatment elsewhere, research staff will do their best to help facilitate this process, and any cost of treatment outside of Michigan Medicine will be the responsibility of the participant. At the participants request, research staff will also confidentially communicate STI results to the participant's health care physician, asking the participant to sign a medical release of information for this purpose. Research staff will also follow-up with non-Michigan Medicine participants to confirm that treatment was received and/or to help identify any obstacles to treatment (e.g., if patient needs additional treatment referrals, etc.).

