4.0. Approach

[figure not shown]
The proposed study is a two-group, randomized, controlled design with an initial session (conducted close to the first prenatal visit), plus two booster sessions within one month later (at 2 and 4 weeks). There will be follow up assessments at 8 and 24 weeks, and at 6 weeks postpartum, conducted by computer and delivered by RA either at the clinic, or remotely over the telephone, or at participants' home. Birth outcome data will be available by postpartum medical records. We will focus on testing the efficacy and utility of the theoretically driven HCEM to target STI risk during pregnancy and postpartum, integrating alcohol and drug use given the well-supported relationship between these risks. The proposed study will use a sophisticated intervention development tool, the Computerized Intervention Authoring Software (CIAS). A technology-delivered intervention approach promotes scientific rigor and greatly facilitates replicability in the community.

4.1. The Health Check-up for Expectant Moms (HCEM) is a brief intervention (one session plus two booster sessions) that is theory-driven and derived from empirical support (see Figure 2, below). Motivational interviewing (MI) has been found to be effective for STI/HIV risk reduction. MI is an intervention approach with wide dissemination and demonstrated efficacy. Consistent with the Self Determination Theory (SDT), MI is a client-centered counseling style that facilitates internal motivation to change through alignment of behavior change with deeply held beliefs,

values, and goals. MI utilizes evolving readiness and self-efficacy to change.

Moreover, the MI model appears to be generalizable to different populations, including low-income urban women. The components of the STI and alcohol/drug use risk reduction to be used in HCEM are formulated to be highly specific to the perinatal setting and entail

Figure 1. Conceptual Model of HCEM Effects and Mechanisms

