(i.e., other changes they have made during pregnancy), thereby countering experiences and perceptions that may make them vulnerable for substance use. Additionally, MI with its collaborative and non-confrontational approach and its emphasis on increasing awareness to successful steps towards their well-being is consistent with recommendations for brief interventions in substance use, including increasing self-efficacy and relapse prevention skill sets to extend into postpartum.

4.2. Preliminary data from R21 Along with two members of this research team, the PI conducted a RCT pilot study of 50 high-risk pregnant women attending prenatal care in a large urban clinic in Providence, RI, with comparable patient demographics to the clinical sites proposed in the current study. The intervention received very high mean ratings of satisfaction (6.3 out of 7), and the computer software was rated highly by both control and the intervention participants (4.6 out of 5). Feedback from the exit interview was positive with participants consistently reporting that they found the intervention educational, interesting, and realistic. The RCT was feasible in terms of recruitment and enrollment of participants. A total of 401 women were screened over the course of nine months, with 34% meeting eligibility criteria. Overall, of the 50 women enrolled for the randomized trial, all 50 completed the intervention session. Forty-nine women (98%) completed the booster session and assessment 4 months later, demonstrating feasibility and uptake of these sessions. Participants in the HCEM condition demonstrated a significantly larger reduction in any self-reported marijuana or alcohol use compared to control condition (time-by-group interaction $p = 0.015$). There was a higher reduction of unprotected sex at follow-up in the intervention arm than control (27% vs. 5%); the direction and magnitude of this effect was very promising and would be of clinical significance, however, was not significant with this small sample size ((OR = 0.17, $p = 0.12$); see Fig 3, right). These encouraging findings strongly support the current application. The lack of significance regarding unprotected sex reduction may also indicate that additional contact may be needed for our high-risk group of pregnant women, supporting a second booster session in the proposed trial.

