For the assessment timepoints that require urine sample collection for STI testing, Michigan Medicine participants have the option to complete STI testing at any Michigan Medicine lab site. For both Michigan Medicine and non-Michigan Medicine participants, they have the option to receive an at-home STI testing kit. The study team will be responsible for mailing the kit to the study participant and covering the cost of returning the kit. Drug testing will no longer be required for study participants (as of November 2022). Instead, the study team will collect the results of already existing drug tests in the patient's chart completed during the duration of their study participation. This will include patients at Luke Clinic, for whom the research team will have guest access to the clinic's Electronic Health Record System, allowing for the collection of patient medical information.

Should an already enrolled participant choose to leave the study or not follow through with appointments for some reason, we will ask them for their feedback through an anonymous and voluntary survey that asks what the research team can do to more easily facilitate women's participation in the study.

Figure 4. Study Timeline

Information-matched control condition: We will use the same, well-validated, attention, time and information-matched control used successfully in our five previous studies with pregnant women, including in the pilot R21 (ratings of acceptability were equally high among intervention and control group participants). The content will consist of a series of questions regarding television show preferences and viewing a brief series of videos of popular entertainers/shows, with subsequent requests for ratings of subjective preference, and will also help to limit inadvertent therapeutic effects that plague control groups in brief intervention research. We will include facts about alcohol/drug use and risky sex during pregnancy, along with informational brochures from NIAAA/CDC that provide face validity.

5.5. Measures: Participants meeting inclusion criteria will complete an assessment session on the iPad iOS. The battery is designed to minimize assessment with the control group in order to take in to account growing concerns regarding the motivational properties of assessment, leading to substantial Type II error in brief alcohol intervention studies. All of the self-report measures included in this study have good psychometric properties (see Table 1, below).

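### The computer's distress notice is tied to completion, so no notice is stated for a woman who answers yes and then quits

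*Combined protocol and SAP*

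**What the plan says.** The relevant text is one paragraph of Section 12.3 (Protection Against Risk).

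- **Right to stop.** "All participants will be told that they can skip any question, test, or quit at any time if they become uncomfortable".
- **The question.** The program asks each participant "if anything the computer has asked or done is making them feel upset right now".
- **The notice.** "The computer program will notify the research team at completion of study if any participant answers yes to this question". The same sentence adds a second notice, for answers that suggest a need or wish for help. It gives that notice no timing of its own.
- **What the notice is for.** The program passes on no answers. It tells staff only that "there is a need to follow-up with the participant verbally to evaluate the need for assistance".
- **Minimum response.** Any participant who indicates distress receives a referral list.

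Other safeguards are stated nearby. Section 12.2 (Adequacy of Protection Against Risks) gives referral information to everyone at each contact. Section 12.3 also provides a licensed clinician as backup during assessments and the intervention phase.

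**The concern.** The question asks about distress at that moment, and its stated purpose is to start a conversation with the participant. The notice that starts the conversation is timed to completion, while the same paragraph invites an uncomfortable woman to stop. A woman who answers yes and then stops has followed her instructions exactly, yet she has not reached the event to which the notice is tied. The trigger is therefore least dependable for someone upset enough to leave.

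What is at stake is participant protection. Section 12.4 rests part of its benefit-risk statement on the distress procedures bringing higher-level care to those who need it, and this trigger is one of those procedures.

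**Working it through.** No arithmetic settles this point and the plan gives no figure to reproduce. The check sets the stated rules side by side.

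**Step 1. What completion means.** The text can be read in two ways.

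| Reading | Woman finishes the session | Woman answers yes, then quits the session |
|---|---|---|
| Completion of the computer session | Notice at the end of the session | No notice stated |
| Completion of the whole trial | Notice only after her last assessment | No notice stated at the time; later only if she completes the trial |

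The first reading is the natural one, because a question about being upset at that moment makes little sense if staff hear of it after the postpartum visit. The right-hand column shows a gap on either reading, so the point does not depend on the choice.

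**Step 2. Whether another sentence fills the gap.** The second notice has no separate timing and no provision for an early exit. The referral list goes to anyone indicating distress with no completion condition, but the text does not say how staff learn of a yes given before an exit. Clinician backup is a resource for responding once distress is known; it is not described as a means of detecting it. No section available for review says that a notice is sent at once or on exit.

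**Step 3. Where a missed notice could matter.**

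| Session | Staff contact described | Question stated to run there |
|---|---|---|
| Baseline (Sections 5.3, 5.4) | Yes: in a clinic room, or by phone and online | Not specified by session |
| Follow-ups (Sections 4.0, 5.4) | Yes: "conducted by computer and delivered by RA either at the clinic, or remotely over the telephone", or at home | Not specified by session |
| Two boosters (Sections 5.0, 5.4) | None: done at home through the study website | Not specified by session |

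At baseline and follow-ups a research assistant would see or hear a woman stop, even without an automated notice. That leaves the boosters as the sessions where the notice would carry most weight, on the condition that the question is asked there.

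**Step 4. Size.** A count of missed notices would need three quantities: how often the question is answered yes, how often a session is left unfinished after a yes, and whether the question runs in the boosters. The protocol gives none of them. The count may be zero.

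**The case against.** The strongest case against is that the point may have no practical setting. Staff contact covers baseline and follow-ups, and nothing shows that the question runs in the boosters. Section 12.3 introduces it in connection with sensitive items, Section 12.2.3 links distress to sensitive questions and STI testing, and Table 1 has no booster column. If the boosters carry no such question, no booster answer can be lost. Boosters are also not outside the safeguards: Section 4.1 counts them as part of the intervention, and clinician backup covers the intervention phase. The moment at which an alert fires is often set in the software or an operating procedure, which may already handle early exits.

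Most of this stands, and it is why the point is small. It does not remove the point, because the protocol is not silent on timing. It states a rule, and that rule, followed as written, sends nothing for a yes followed by an exit.

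A reader might infer four stronger things that the document does not support:

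- **That distressed women are left without protection.** Referral information, clinician backup and staff contact all remain.
- **That the upset question is the only possible signal in a home session.** The second notice is a further possible signal, and its timing is unclear.
- **That the anonymous survey in Section 5.4 is the stated response to distress.** It is a feedback tool for women who leave the study or miss appointments. Quitting one session is not leaving the study, and the survey excludes no other contact.
- **That pilot booster completion (Section 4.2) or the worst-case drop-out of 20% (Section 7.4) gives the number affected.** Neither measures mid-session exits after a yes, and a session that is never opened asks no question.

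**Conclusion.** The point holds in a narrow form and is minor. Section 12.3 ties the computer's distress notice to an ambiguous completion event and states no notice for a woman who answers yes and then quits. No endpoint, analysis or conclusion of the trial is affected.

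This rests on two assumptions. The first is that the notice works as the text describes; the software may already send it earlier, and the document does not show this either way. The second is that no text unavailable for review covers early exits. Practical importance also depends on whether the question runs in the home boosters. If it does, the gap falls in sessions with no described staff contact. If it does not, staff contact at the other study sessions largely covers it.

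**What to change.** In Section 12.3, replace the completion wording with: *when the answer is entered, and at the latest when the computer session ends, whether finished or quit*. Apply it to both notices in that sentence, and to the home boosters if the question runs there.

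The cost is one sentence of protocol text, possibly one software setting, and a few extra verbal follow-ups. The change does not reach a woman who stops before the question is shown; for her, the existing referral information and staff contact remain the safeguards.
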